### **2.7. Primary and feasibility outcomes**

The primary outcome measure is the follow-up rate (i.e., number of participants that completed the program and attended follow-up). Other feasibility outcomes include: acceptability (content, format, frequency, and duration) of the Pain Informed Movement program compared to the control group, recruitment rate, burden of procedures, adherence rate (i.e., number of participants that attended all in-person sessions), compliance to the program (i.e., number of participants that reported completion of at least three exercise sessions per week), and AEs. A priori success criteria will be used to determine feasibility and acceptability of the programs (Table 2).

Table 2:

*A priori* feasibility criteria.

Outcome	A priori criteria		
	Proceed	Proceed with protocol amendments	Significant amendments required
Follow up	≥90% of participants followed up at 8 weeks	≥50% of participants followed up at 8 weeks	≤50% of participants followed up at 8 weeks
Recruitment	≥40 participants consent to participate/year	≥30 participants consent to participate/year	<30 participants consent to participate/year
Compliance to exercise program	≥80% of participants report exercise at least 3 times a week	≥50% of participants report exercise at least 3 times a week	<50% of participants report exercise at least 3 times a week
Program content acceptability – usefulness	≥50% found treatment useful (Likert ≥4/5)	≥25% found treatment useful (Likert ≥4/5)	<25% found treatment useful (Likert ≥4/5)
Program content acceptability – frequency	≥50% found frequency acceptable (Likert ≥4/5)	≥25% found frequency acceptable (Likert ≥4/5)	<25% found frequency acceptable (Likert ≥4/5)
Program content acceptability – duration	≥50% found duration acceptable (Likert ≥4/5)	≥25% found duration acceptable (Likert ≥4/5)	<25% found duration acceptable (Likert ≥4/5)
Format acceptability – delivery	≥50% found treatment delivery (in-person and home) acceptable (Likert ≥4/5)	≥25% found treatment delivery acceptable (Likert ≥4/5)	<25% found treatment delivery acceptable (Likert ≥4/5)
Adherence to in person treatment	≥75% of participants attended all in person treatment sessions	≥50% of participants attended all in person treatment sessions	≤25% of participants attended all in person treatment sessions
Burden (0 = no burden, 10 = most burden)	Burden of completing questionnaires and physical tests <3/10 for ≥75% of participants	Burden of completing questionnaires and physical tests <3/10 for ≥50% of participants	Burden of completing questionnaires and physical tests <3/10 for ≤25% of participants
Adverse events	No adverse events or only mild transient (e.g., pain increase) for ≥75% of participants	No adverse events or only mild transient (e.g., pain increase) for ≥50% of participants	No adverse events or only mild transient (e.g., pain increase) for ≤25% of participants

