## **2.2. Study participants**

Sample size is based on the primary outcome of complete follow-up using the confidence interval method for calculating sample size in pilot trials [20]. We will aim for 90% follow-up but will consider the trial successful if we achieve 81%. To achieve a margin of error of 9%, with 10% added for attrition, we will require 66 participants (n ¼ 33 per arm).

Participants will be recruited through the email lists of the McMaster University's community and research centers and their social media pages. Additionally, the study poster will be placed on other social media channels (e.g., Twitter, Facebook advertisements) and flyers will be placed in local Orthopaedic surgeon, Rheumatologist, and Psychiatrists offices.

The inclusion and exclusion criteria are listed in Table 1.

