**Table 1**  
Inclusion and exclusion criteria.

Inclusion criteria	Exclusion criteria

≥40 years of age with diagnosis of knee osteoarthritis (KOA by) a physician
 
OR ≥45 years of age and having
 
activity-related knee joint pain with or without morning stiffness lasting ≤30 min (NICE criteria)
 
2 Having an average pain intensity of at least 3/10 on a numeric pain scale on most days of the past month
	
1 Cannot communicate in English
 
3 Has inflammatory arthritis or other systemic conditions
 
4 Has had lower limb trauma or surgery within the past 6 months
 
5 Has participated in a KOA exercise program in the past 3 months
 
1 Has had any injection in the index knee within 3-months prior to baseline assessment
 
2 Does not have regular access to the internet
 
3 Inability to get up and down from the floor independently
 
4 Use of mobility aids
 
5 Currently participating in any other drug/device/exercise clinical trial related to OA
 
6 Planned absences (e.g., trips away) of >1 week
 
7 Currently receiving other forms of care for KOA pain (e.g., from a physiotherapist, chiropractor, athletic therapist, kinesiologist)
 
8 Does not meet screening for safe participation in exercise according to the Get Active questionnaire from the Canadian Society for Exercise Physiology [25]

[figure not shown]

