### 2.5.1. Pain Informed Movement program

Participants in this group will receive an 8 week in-person group exercise program held twice weekly, in which they will receive exercise instructions and PNE. They will also be

asked to complete a third exercise session at home weekly. Participants will be provided with tracking sheets to note their compliance and progress.

The PNE component will consist of several short videos that are provided online for the first five weeks of the program (the videos are divided into short segments, each with a separate subject, totaling 20–30 min/week)). The videos will provide simple explanations of nociception processing by the nervous system, how it can be modulated through upregulation or downregulation of signals to increase or decrease pain and that pain does not accurately signify the extent of tissue damage, particularly when experiencing chronic pain. The videos will also offer techniques to reconceptualize pain and movement not as imminently dangerous. In addition, the videos will introduce and provide a demonstration of mind-body techniques that will be provided progressively each week. The mind-body techniques will include breath awareness and regulation, body awareness and muscle tension regulation, and awareness of pain related thoughts and emotions. The techniques will then be implemented in the in-person exercise sessions where participants are asked to incorporate them into their performance of the exercises. Instructions will be provided on how to ‘nudge the edge’ of pain which is conceptualized as a balance between challenging current physical abilities during the exercises and being successful at not leaving pain provoked and/or function limited after exercise. Participants will be instructed to use breath, body tension, thoughts, and emotions as guideposts to their pain in order to successfully nudge its edge. Participants will be given the opportunity to ask questions during the in-person sessions.

The exercise component (75 min) will consist of three parts (in sequence):

Part one: the first part is the warm-up which begins with a centering practice aimed at regulating physiology. Next, warming movements of the shoulders, legs, and spine will be instructed.

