### **2.5.2. Neuromuscular exercise and standard OA education**

Participants in this group will receive an 8-week in-person group exercise program held twice weekly, in which they will receive exercise instructions and standard OA education. Participants will be provided with tracking sheets to note their compliance and progress.

The exercise component (60 min) of this group will be similar to that of the other group without the added mind-body techniques. Similarly, a third home session (weekly) will be facilitated by exercise handout sheets. The exercise instructions will be delivered by a physiotherapist. The standard OA education will consist of several short videos (20–30 min/week for the first two weeks provided through online videos) and will cover the following topics: pathophysiology of OA, common OA symptoms, risk factors, the effects of exercise, and self- management tips. Participants will be given the opportunity to ask questions during the in-person sessions.

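### Adherence means attending all 16 classes, although Table 1 admits people with planned absences of up to a week, so a well-attended program can miss 'Proceed'; the same Table 2 row leaves 25–50% unclassified

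*Combined protocol and SAP*

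**What the plan says.** Section 2.7 defines the measure as "adherence rate (i.e., number of participants that attended all in-person sessions". Table 2 sets three bands on it:

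- *Proceed*: "≥75% of participants attended all in person treatment sessions"
- *Proceed with protocol amendments*: "≥50% of participants attended all in person treatment sessions"
- *Significant amendments required*: "≤25% of participants attended all in person treatment sessions"

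The number of classes follows from the intervention sections. Section 2.5.1 states "Participants in this group will receive an 8 week in-person group exercise program held twice weekly", and section 2.5.2 says the same of the control arm: "Participants in this group will receive an 8-week in-person group exercise program held twice weekly". In both arms, attending all sessions means 16 of 16.

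Among the exclusions in Table 1 is "Planned absences (e.g., trips away) of" more than one week. Shorter planned absences do not exclude.

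The documents describe no make-up class and no excused-absence rule. They give no expected attendance rate, and they do not say whether adherence is taken over all randomized participants or over completers. Section 2.11 reports feasibility outcomes descriptively.

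**The concern.** The score is all-or-none per participant. Someone who misses one class of 16 counts the same as someone who stops coming after the first week. Eligibility and outcome also pull apart: a person with a known week away may enter, and if that week covers even one class, they cannot be adherent as defined.

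Adherence is named in objective 2, and section 2.7 says the Table 2 criteria will be used to determine feasibility. If the rule responds to isolated misses rather than to how much of the program people attend, the trial could report a need for amendments to a program that most participants attended almost completely. It could also land in the part of the row that gives no verdict.

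**Working it through.** **Inputs from the documents.** Classes per participant: 8 × 2 = 16 (sections 2.5.1 and 2.5.2). Participants: 66 (section 2.2), used here only as the denominator, on the assumption that all randomized participants are counted. *Proceed* bar: 75% (Table 2). The plan gives no derivation for this bar, so there is no figure of its own to reproduce.

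**Assumptions.** Attendance rates per class, and the degree to which misses cluster within people, are not in the documents. They are varied below.

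**Step 1: no model.** 0.75 × 66 = 49.5, so *Proceed* needs at least 50 participants with perfect attendance, and 17 without it are enough to miss it (49/66 = 74.2%).

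- Total class places: 66 × 16 = 1,056.
- 17 people miss one class each: (1,056 − 17)/1,056 = 98.4% overall attendance, and *Proceed* is missed.
- 17 people miss two classes each, the most a one-week absence would cost on two classes a week: (1,056 − 34)/1,056 = 96.8%, and *Proceed* is missed.

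**Step 2: independent misses.** The share attending all 16 is p^16, where p is attendance per class. For 75%, p = 0.75^(1/16) = 0.982. The chance of *Proceed* is P(X ≥ 50) for X ~ Binomial(66, p^16).

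| Attendance per class | Attend all 16 | Chance of *Proceed* |
|---|---|---|
| 90% | 18.5% | about 0 |
| 95% | 44.0% | <0.0001 |
| 97% | 61.4% | 0.01 |
| 98% | 72.4% | 0.32 |
| 98.5% | 78.5% | 0.76 |
| 99% | 85.1% | 0.99 |

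**Step 3: clustered misses.** Beta-binomial with mean attendance m and intra-person correlation (ICC) ρ; parameters a = m(1/ρ − 1) and b = (1 − m)(1/ρ − 1).

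| Mean attendance | ICC | Attend all 16 | Chance of *Proceed* |
|---|---|---|---|
| 95% | 0.1 | 61.6% | 0.01 |
| 95% | 0.2 | 70.6% | 0.22 |
| 95% | 0.3 | 76.5% | 0.62 |
| 95% | 0.5 | 84.3% | 0.98 |
| 90% | 0.2 | 49.4% | about 0 |
| 90% | 0.3 | 58.2% | 0.002 |
| 90% | 0.5 | 70.7% | 0.22 |

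At 95% attendance the answer changes between ICC 0.2 and 0.3.

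**Step 4: the bands.** The middle band starts at 50% and the lowest ends at 25%. With 66 participants, 16 is 24.2%, 17 is 25.8%, 32 is 48.5% and 33 is 50.0%, so any count from 17 to 32 has no category. Two of the results above fall there: 44.0% (95% attendance, independent) and 49.4% (90% attendance, ICC 0.2).

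**Step 5: an illustrative threshold of at least 14 of 16.** Over ICC 0 to 0.3:

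- 95% attendance: 89% to 96% would be adherent.
- 90% attendance: 76% to 79% would be adherent, and the chance of reaching 50 of 66 is 0.56 to 0.79.

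**The case against.** The strongest reply is that the outcome turns on inputs the documents do not supply. If absences concentrate in a few people, 95% attendance with ICC 0.3 or more reaches the bar. This stands: a reader might infer from the independent-miss figures that the trial is likely to miss *Proceed*, but the documents give neither an attendance rate nor a clustering value, so only the conditional statement is supported.

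Second, a planned absence of up to a week may overlap two classes, one or none, the number of such participants is unknown, and eligibility criteria need not guarantee adherence. This also stands. Table 1 and Table 2 are in tension, not in formal contradiction.

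Third, the consequence is limited. Adherence is a secondary feasibility outcome, it is analysed descriptively, and missing *Proceed* leads at most to an amendment category, not to stopping. That limits the weight of the point. It does not remove it, because the bands are the stated basis for judging feasibility.

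Two stronger readings are tempting and should not be drawn:

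- *That the rule cannot tell a well-attended program from an abandoned one.* It can. At an assumed 50% mean attendance with ICC 0.2, about 2% would attend all 16, against 44% to 71% at 95% attendance (ICC 0 to 0.2). The primary follow-up outcome also counts program completion.
- *That the compliance row is inconsistent because its 80% bar lies above the 75% adherence bar.* This would require that three sessions be completed in every single week and that extra home sessions cannot replace a missed class. The documents state neither.

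**Conclusion.** The point holds in conditional form. As defined, adherence is perfect attendance at 16 classes, while eligibility admits people who may already expect to miss up to two. The rule can deny *Proceed* to a well-attended program. The assumption-light demonstration is 17 of 66 participants missing one class each, at 98.4% overall attendance; it needs only that all 66 are counted.

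How probable this is depends on assumed values. With independent misses the bar needs 98.2% attendance per class. At 95%, perfect attendance runs from 44% (independent) to 71% (ICC 0.2), and passes 75% from about ICC 0.3.

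The gap between 25% and 50% in the same row depends on no assumption; it is in the text of Table 2.

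**What to change.** Before any data are seen:

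1. In section 2.7 and the Table 2 adherence row, replace attendance at all sessions by a per-participant threshold compatible with Table 1, for example at least 14 of the 16 classes, which accommodates a one-week absence.
2. Report the mean percentage of classes attended, and keep full attendance as a descriptive figure.
3. Make the bands exhaustive, for example by setting *Significant amendments required* at below 50%.

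The edit is one definition and one table row. Scoring full attendance already requires knowing whether each class was attended, so little or no extra data collection should be needed, although the documents mention only participant tracking sheets.

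The cost is a less strict criterion, which is why it must be fixed in advance. The cut at 14 is a judgement: at 90% attendance only 76% to 79% would be adherent (ICC 0 to 0.3), just above the bar, so *Proceed* would still not be assured.

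### Table 2 gives no verdict for adherence, burden or adverse-event results between 25% and 50%

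*Combined protocol and SAP*

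**What the plan says.** Section 2.7 gives Table 2 a decision role: "A priori success criteria will be used to determine feasibility and acceptability of the programs". Each of its ten rows has three columns: proceed, proceed with protocol amendments, and significant amendments required.

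Three rows share one pattern, with at least 75% in the first column, at least 50% in the second and at most 25% in the third:

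- Adherence: the second column is "≥50% of participants attended all in person treatment sessions" and the third is "≤25% of participants attended all in person treatment sessions".
- Burden: the third column is "Burden of completing questionnaires and physical tests <3/10 for ≤25% of participants".
- Adverse events: the third column is "No adverse events or only mild transient (e.g., pain increase) for ≤25% of participants".

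Other rows are built so that the second and third columns meet. The compliance row ends with "<50% of participants report exercise at least 3 times a week" directly below a middle bound of at least 50%. The four acceptability rows end at below 25%, directly below a middle bound of at least 25%. Recruitment uses at least 30 and below 30 per year.

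Section 2.11 adds only that feasibility outcomes will be reported descriptively. No section says what to conclude when no column is met, and none states the denominator for the percentages.

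**The concern.** Criteria fixed in advance are meant to settle the verdict before anyone knows the result. In these three rows a result between 25% and 50% fails both columns that allow the trial to proceed, yet does not reach the column that calls for significant amendments.

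The table itself supports two opposite repairs. By analogy with compliance, the result would mean significant amendments. By analogy with the acceptability rows, it would mean proceeding with amendments. The choice would be made with the data in hand.

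This matters most for adherence, because section 2.7 defines it on an all-or-nothing basis: "adherence rate (i.e., number of participants that attended all in-person sessions"). Two sessions a week for eight weeks makes 16, and missing one is enough to fail. Table 1 excludes only planned absences of more than one week, so an eligible participant can be away for a week, miss up to two sessions, and count as non-adherent. A programme with good average attendance can therefore produce a low share of full attenders.

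**Working it through.** **Step 1. Coverage of the ten rows.** Each row was checked for values that meet no column and values that meet both the second and the third.

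| Row | Second column | Third column | Result |
|---|---|---|---|
| Follow-up | ≥50% | ≤50% | no gap; exactly 50% meets both |
| Recruitment | ≥30/year | <30/year | contiguous |
| Compliance | ≥50% | <50% | contiguous |
| Acceptability (4 rows) | ≥25% | <25% | contiguous |
| Adherence | ≥50% | ≤25% | gap between 25% and 50% |
| Burden | ≥50% | ≤25% | gap between 25% and 50% |
| Adverse events | ≥50% | ≤25% | gap between 25% and 50% |

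Three rows have a gap, six are contiguous, and one overlaps at a single point. The gap is open at both ends: exactly 25% and exactly 50% do have a verdict.

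**Step 2. The gap in participants.** These are the counts k with 0.25 < k/n < 0.50. Section 2.2 gives n = 66 in total and 33 per arm; n = 60 illustrates roughly 10% attrition.

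| n | Unclassified counts | As % | Share of possible counts |
|---|---|---|---|
| 66 | 17–32 | 25.8–48.5 | 16 of 67 |
| 60 | 16–29 | 26.7–48.3 | 14 of 61 |
| 33 | 9–16 | 27.3–48.5 | 8 of 34 |

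**Step 3. Can adherence land there?** The documents give no attendance rate and no within-person correlation, so everything in this step is an assumption. Let m be per-session attendance and q the share attending all 16 sessions.

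- Independent sessions: q = m^16. Examples: 0.93^16 = 0.313 and 0.95^16 = 0.440. The gap edges are 0.25^(1/16) = 0.917 and 0.50^(1/16) = 0.958.
- Attendance correlated within person (beta-binomial with correlation ρ): a = m(1−ρ)/ρ, b = (1−m)(1−ρ)/ρ, and q is the product of (a+j)/(a+b+j) over j = 0 to 15. Example: m = 0.90 and ρ = 0.1 give a = 8.1, b = 0.9 and q = 0.373.

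The expected share q lies in the gap when m is 91.7%–95.8% (independence), 86.1%–92.9% (ρ = 0.1) or 80.9%–90.2% (ρ = 0.2).

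The chance of an unclassified result with 66 participants is P(17 ≤ X ≤ 32), where X is binomial(66, q):

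| Assumption | m | q | Chance unclassified |
|---|---|---|---|
| Independent | 90% | 0.185 | 0.09 |
| Independent | 93% | 0.313 | 0.87 |
| Independent | 95% | 0.440 | 0.80 |
| Independent | 97% | 0.614 | 0.02 |
| ρ = 0.1 | 85% | 0.222 | 0.29 |
| ρ = 0.1 | 90% | 0.373 | 0.96 |
| ρ = 0.1 | 93% | 0.505 | 0.42 |
| ρ = 0.1 | 95% | 0.616 | 0.02 |
| ρ = 0.2 | 85% | 0.342 | 0.94 |
| ρ = 0.2 | 90% | 0.494 | 0.49 |
| ρ = 0.2 | 93% | 0.613 | 0.02 |

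Stronger correlation moves the risk to lower attendance. At 90% attendance the chance is 0.07 for ρ = 0.3 and 0.004 for ρ = 0.4; at 85% it is 0.81 and 0.32.

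**Step 4. The follow-up overlap.** It needs exactly 33 of 66. The binomial probability is 0.0003 at a true rate of 70% and about 1e-8 at 81%.

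**The case against.** The strongest reply is that little hangs on this. The primary outcome is the follow-up rate, and its row has no gap. The three affected rows are secondary feasibility criteria, reported descriptively, and no rule combines the ten rows into one decision. A result in the gap already fails both columns that allow the trial to proceed, so a reader may naturally take it as calling for significant amendments.

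The limit on consequence stands, and it keeps this from being a critical point. The natural reading does not close the gap: the third column says at most 25% in so many words, and the acceptability rows show that the same table can place results of 25% to 50% in the middle column.

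The second reply is that the probabilities rest on invented attendance figures and span almost the whole range from 0 to 1. That is fair. They show that the gap is reachable for adherence at ordinary-looking attendance, and nothing stronger. They say nothing about burden or adverse events, for which no likelihood is claimed. The gap itself does not depend on them.

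The third reply is that the follow-up overlap and the missing denominator are side issues. That is also right. The overlap is negligible in probability and reading the columns from left to right resolves it. The gap exists whatever the denominator.

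**Conclusion.** The concern holds. Three of the ten feasibility criteria give no verdict for results strictly between 25% and 50%, which is 17 to 32 of 66 participants, and no other section supplies one. This follows from the printed bounds alone and needs no assumption. The practical weight falls on adherence, where an all-16-sessions definition makes the band plausible; how likely it is depends on attendance figures the documents do not give. It should be corrected, but it does not affect the primary outcome.

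**What to change.** Before results are seen, make the bands contiguous and non-overlapping.

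- **Adherence and burden:** either change the third-column bound from at most 25% to below 50% (the compliance pattern, stricter), or lower the middle bound to at least 25% and set the third to below 25% (the acceptability pattern, more lenient). Either closes the gap; the choice is the sponsor's.
- **Adverse events:** reconcile the two bounds so that every result has exactly one verdict.
- **Follow-up:** change at most 50% to below 50% in the third column.
- **Denominator:** add one sentence saying whether the percentages are of all randomised or of those followed up, and whether overall or per arm.

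The all-sessions definition of adherence can stay. Mean sessions attended out of 16 may be reported alongside it descriptively.

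The cost is a few table cells and one sentence, with no new data. The downside is that results with no verdict today acquire one: significant amendments under the stricter option, proceeding with amendments under the lenient one.

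The documents do not settle whether data have already been seen (Table 3 is in the past tense, most of the Methods in the future tense). If they have, the gap should be disclosed and the percentages reported without a verdict presented as pre-specified.

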## **2. Methods**

### **2.1. Study design**

This is a pilot study with a nested qualitative component designed as a parallel, randomized, single-centre, two-arm clinical trial with a 1:1 allocation ratio. Informed consent will be obtained from all participants prior to initiating the study. All participants will be invited to complete an exit survey and take part in focus group interviews at program completion. Fig. 1 depicts the trial design. The procedures will be followed in accordance with the ethical standards of the responsible committee on human experimentation (institutional and national) and with the Helsinki Declaration of 1975, as revised in 2000. The Conceptual Framework for Defining Feasibility [17] and Pilot studies and the Standard Protocol Items: Recommendations for Intervention Trials will be used [18]. Following

program completion, the study results will be reported using the extended CONSORT guideline for pilot trials as well as the TiDIER guidelines [17,19]. The study protocol is registered at [clinic trials.gov #NCT05730829](https://clinicaltrials.gov/ct2/show/NCT05730829).

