### **2.6. Safety**

Participants will be provided with a tracking sheet to note any adverse events (AEs) throughout the study. The instructors will also monitor for adverse events during the in-person sessions. If any AE happens, participants will be instructed to tell the instructor to modify the exercises or reduce the intensity if necessary. AEs will be defined as any problem that lasts for >2 days and/or causes the participant to seek other treatment.

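### The adverse-event row of Table 2 ignores seriousness and relatedness, so one or a few serious, intervention-related events leave it at Proceed

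*Combined protocol and SAP*

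**What the plan says.** Section 2.7 makes Table 2 the pre-specified test of whether the programs are feasible and acceptable. Its adverse-event row has three bands, all defined by the share of participants at or below one level of harm:

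- *Proceed*: "No adverse events or only mild transient (e.g., pain increase) for ≥75% of participants"
- *Proceed with protocol amendments*: "No adverse events or only mild transient (e.g., pain increase) for ≥50% of participants"
- *Significant amendments required*: "No adverse events or only mild transient (e.g., pain increase) for ≤25% of participants"

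Section 2.6 gives the definition: "AEs will be defined as any problem that lasts for >2 days and/or causes the participant to seek other treatment". It provides tracking sheets and instructor monitoring during classes, and states one response: "If any AE happens, participants will be instructed to tell the instructor to modify the exercises or reduce the intensity if necessary".

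The protocol contains no definition of a serious event, no severity grading, no assessment of relatedness and no separate criterion for serious events. It does not say whether the row is applied to both arms together or to each arm, or how the rows of Table 2 are combined.

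**The concern.** The row has the same form as the acceptability rows: a percentage of participants for whom the result was satisfactory. That form suits opinions about class frequency or duration. It suits harm less well, because the question is not only how many participants had more than a minor problem but also how bad the worst problems were and whether the study caused them. Everything beyond mild and transient falls into one remainder, and only the size of that remainder counts.

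Serious events in an exercise trial are expected to be few, and a percentage band with a 25% allowance cannot register a few. If one participant had a fracture or a hospital admission that was plausibly due to study exercise, the row would read *Proceed*, the column without amendments, just as it would with no such event. The team would then have to decide after seeing the data whether to follow its own criterion, which is what a criterion fixed in advance is meant to avoid.

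**Working it through.** **Inputs.** Planned size: "we will require 66 participants", 33 per arm (section 2.2), in a "two-arm clinical trial with a 1:1 allocation ratio" (section 2.1). Row thresholds of 75% and 50% for adverse events; *Proceed* thresholds of 90% for follow-up, 80% for compliance and 75% for adherence (Table 2).

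**The plan's own figure.** The confidence-interval formula is n = z²p(1−p)/m². With p = 0.90, m = 0.09 and 95% confidence (assumed; the level is not stated), n = 1.96² × 0.90 × 0.10 / 0.09² = 42.7, so 43. With 10% attrition, 43/0.90 = 47.8, so 48. This does not reproduce 66. The discrepancy does not affect the present point, which takes the planned 66 as given; smaller denominators are shown below.

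**Step 1: what the row allows.** Needed for *Proceed* = 0.75 × N, rounded up. Allowed with worse events = N minus that number.

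| Denominator | Needed | Allowed with worse events |
|---|---|---|
| 66 (all planned, pooled) | 49.5 → 50 (75.8%) | 16 (24.2%) |
| 60 | 45 (75.0%) | 15 (25.0%) |
| 59 (about 10% fewer than 66) | 44.25 → 45 (76.3%) | 14 (23.7%) |
| 33 (each arm) | 24.75 → 25 (75.8%) | 8 (24.2%) |

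For the middle band at N = 66, 0.50 × 66 = 33 are needed, so 33 may have worse events.

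Pooling matters. If the row is pooled, all 16 could be in one arm (16/33 = 48.5%) and the row would still read *Proceed*. Applied per arm, the limit in that arm would be 8.

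**Step 2: what one or a few events do.** Each participant is 1/66 = 1.5 percentage points. If one participant has a serious related event and nobody else exceeds mild transient, the row stands at 65/66 = 98.5%. With three such participants it is 63/66 = 95.5%. It takes 17 participants to leave *Proceed* (49/66 = 74.2%). A single event therefore changes the row only if 16 others already have worse events.

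**Step 3: whether another row would respond.** At N = 66:

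- Follow-up: 0.90 × 66 = 59.4, so 60 are needed and 6 may be lost. A seventh loss gives 59/66 = 89.4% and removes *Proceed*.
- Adherence: 50 must attend all classes, so 16 may miss one or more.
- Compliance: 0.80 × 66 = 52.8, so 53 are needed and 13 may fall short.

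These rows count participation. A serious event enters them only if the participant stops taking part or misses sessions, and it then counts as one participant. One withdrawal, with everyone else meeting the criterion, leaves each row at 65/66 = 98.5%.

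**The case against.** The strongest reply is that a reader might infer more from this row than the documents support. Five parts of that reply stand.

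- **Other rows.** A reader might infer that 16 participants could have serious events and the trial would still go ahead unamended. If all 16 dropped out, follow-up would be 50/66 = 75.8%, which falls in the amendment band; 7 losses are enough to remove *Proceed* there. Many serious events would probably show up in this way. One or a few would not.
- **What the row decides.** A reader might infer that Table 2 is the gate to a larger trial. Section 2.7 gives it only the task of judging feasibility and acceptability. No larger trial is named, and nothing makes one row's result the result of the whole table.
- **The lower boundary.** A reader might infer that a strain lasting a few days weighs the same as a fracture. That cannot be shown. Mild and transient is not defined, and since an event must last more than 2 days or lead to other treatment to count at all, such a strain may well be classed as mild transient.
- **Visibility and prior risk.** Adverse events are a listed feasibility outcome, to be reported descriptively (sections 2.7 and 2.11). Reporting will follow the pilot-trial extension of CONSORT (section 2.1), the ethics board may access records (section 2.10), and candidates are screened for safe exercise (Table 1). Events would not be hidden. None of this, however, alters how the row is scored.
- **Format.** Any percentage criterion gives each participant the same small weight, so 1.5 points is not an error in itself. It matters here because no seriousness criterion accompanies the percentage.

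It can also be said that an override adds only documentation, since the row may still be scored *Proceed* after review. That is true. The gain is that the judgement is committed to in advance and recorded.

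**Conclusion.** The point holds for the score of the adverse-event row. As written, one or a few serious, intervention-related events leave it at *Proceed*, and no other row would reliably respond to them. Up to 16 of 66 participants, or 8 of 33 in each arm, may have worse events of any severity before the score changes. Those counts assume that all planned participants are in the denominator; with 59 or 60 the pooled limit is 14 or 15.

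The documents do not show that the whole trial would be declared ready with such events in the data, or that individual events would be mishandled while the trial runs. The row is a scoring rule, and it affects no estimate or analysis of the secondary outcomes. This is a cheap improvement to a stated decision rule.

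**What to change.** Keep the percentage bands and make these changes:

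1. Add one override to the adverse-event row: if any serious adverse event is judged possibly related to study exercise or procedures, the row may not be scored *Proceed* until the event has been reviewed and the decision on a protocol amendment documented.
2. Add seriousness, with a standard definition, and relatedness to the adverse-event form.
3. Have relatedness judged by an existing team member who neither delivers the classes nor acts as a blinded assessor. Judging whether study exercise caused an event could reveal allocation to an assessor. The protocol does not identify someone for this task, so the role should be stated.
4. State whether the row is applied per arm or pooled.

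The cost is a few sentences, including the definition of seriousness and the standard for relatedness, and two more fields to complete for each event. The downside is that one related serious event delays an unamended *Proceed* until it has been reviewed. The override governs scoring only and changes nothing in how participants are treated or exercised.
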